			Estimate	Confidence limit	Confidence limit
Auto/Auto treatment arm vs					
Auto/Maintenance arm ¹					
Auto/Auto treatment arm vs Auto/RVD					
arm ¹					
Auto/RVD treatment arm vs					
Auto/Maintenance arm ¹					
Risk strata—High risk vs					
Risk strata—Standard risk					
Permanent discontinuation of					
lenalidomide					
(other adjustment factor as needed)					
(other adjustment factor as needed)					
(other adjustment factor as needed)					

[figure not shown]
¹ P-values are compared to the 0.05/3 significance level.

Figure: A forest plot for the hazard ratios and confidence intervals may also be provided.

Supplemental Exhibit 07LT-6: Landmark Analysis of PFS

Figure template for illustration only

Kaplan Meier Estimates and 95% Confidence Intervals

	Lenalidomide taken at 4 years post randomization	Lenalidomide not taken at 4 years post randomization
5-year Estimates:	XX.X (XX.X, XX.X)	XX.X (XX.X, XX.X)

Log-Rank Test for Group Differences

[figure not shown]
Comparison	N	Total Number with an Event	p-value ¹
Lenalidomide use at 4 years			
Yes	xxx	XXX	
No	xxx	XXX	0.XX

¹Significance level is 0.05.

Supplemental Exhibit 07LT-7: Landmark Analysis of OS

Figure template for illustration only

Overall Survival by 4-Year Lenalidomide Status

Kaplan Meier Estimates and 95% Confidence Intervals

	Lenalidomide taken at 4 years post randomization	Lenalidomide not taken at 4 years post randomization		
5-year Estimates:	XX.X (XX.X, XX.X)	XX.X (XX.X, XX.X)		

Log-Rank Test for Group Differences

[figure not shown]
Comparison	N	Total Number with an Event	p-value ¹
Lenalidomide use at 4 years			
Yes	xxx	XXX	
No	XXX	XXX	0.XX

¹Significance level is 0.05.

Supplemental Exhibit 07LT-8: Landmark Analysis of EFS

Figure template for illustration only

Event-Free Survival by 4-Year Lenalidomide Status

Kaplan Meier Estimates and 95% Confidence Intervals

	Lenalidomide taken at 4 years post randomization	Lenalidomide not taken at 4 years post randomization		
5-year Estimates:	XX.X (XX.X, XX.X)	XX.X (XX.X, XX.X)		

Log-Rank Test for Group Differences

			First Event			
Comparison	N	Total Number with an Event	PRG or NPT	SPM	ртн	p-value ¹
Lenalidomide use at 4 years						
Yes	XXX	XXX	XXX	XXX	XXX	
No	XXX	XXX	XXX	XXX	XXX	0.XX

¹Significance level is 0.05.

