#### **2.3.2. Patient Eligibility Criteria for Optional Long-term Lenalidomide Maintenance Therapy**

Patients fulfilling the following criteria will be eligible to provide continued long-term follow-up data AND receive long-term lenalidomide maintenance therapy as part of this study:

1. Enrolled and randomized to BMT CTN 0702
2. Completion of 3 years of maintenance therapy on BMT CTN 0702
3. Registered in the mandatory Revlimid REMS® program (formerly the RevAssist® for Study Participants (RASP) program), and be willing and able to comply with the requirements of the Revlimid REMS® program, including counseling, pregnancy testing, and phone surveys.
4. Signed informed consent form.
5. Patients with the ability to speak English or Spanish are eligible to participate in the HQL component of this trial.

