#### **2.3.3. Patient Exclusion Criteria for Long-term Lenalidomide Maintenance Therapy**

Patients who meet any of the following criteria will be ineligible to receive long-term lenalidomide maintenance therapy as part of this study\*:

1. Patients who have evidence of disease progression prior to enrollment (see Section 3.1 for disease progression definition).

---

\* All patients will be followed for long-term outcomes.

2. Patients who were discontinued from BMT CTN 0702 lenalidomide maintenance therapy, for any reason, prior to the completion of the 3 years of 0702 maintenance.
3. Female patients who are pregnant (positive -BetaHCG) or breastfeeding.
4. Females of childbearing potential (FCBP) or men who have sexual contact with FCBP unwilling to use contraceptive techniques (Appendix B) during the length of lenalidomide maintenance therapy.
5. Patients who experienced thromboembolic events while on full anticoagulation during prior therapy with lenalidomide.
6. Patients unwilling to take DVT prophylaxis.
7. Patients who developed a second primary malignancy, excluding non-melanoma skin cancers after initiation of lenalidomide maintenance therapy on BMT CTN 0702.

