1.2.2 Accrual Plan and Randomization

Participants were eligible to accrue on to BMT CTN 07LT as soon as they finished the earlier of 3 years of maintenance therapy on BMT CTN 0702 or four years of follow up on BMT CTN 0702. The protocol was approved after some participants had already finished 3 years of maintenance on BMT CTN 0702 so they were eligible to enroll when the protocol was activated, and there may have been a period when the participant was on commercially-available lenalidomide or other treatment. The protocol was activated in March 2015, and accrual was targeted through the beginning of 2018 to allow a window of time after the last person enrolled on BMT CTN 0702 would be eligible for BMT CTN 07LT.

Randomization occurred on the parent BMT CTN 0702 trial, which had a 1:1:1 randomization ratio with permuted blocks. Randomization on the parent trial was also stratified by patient risk and center. There was no additional randomization on BMT CTN 07LT.

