4.1 Analysis of the Primary Endpoint

The primary analysis of PFS will include all randomized subjects from the BMT CTN 0702 protocol, classified according to their randomized treatment allocation, irrespective of treatment received [intent-to-treat]. The time to this event is the time from randomization on the BMT CTN 0702 protocol to progression, initiation of non-protocol anti-myeloma therapy (this includes lenalidomide if the dose is above 15mg), or death from any cause reported on BMT CTN 0702, BMT CTN 07LT, or to the CIBMTR. Patients will be censored at loss to follow-up or end of 2018, whichever comes first. For those lost to follow-up, if loss occurred during 0702, censoring will occur at last myeloma evaluation before loss to follow-up. For those lost to follow-up on BMT CTN 07LT, censoring will occur at the last contact date reported on the study status follow-up form. For those who completed BMT CTN 0702 but did not enroll on 07LT, censoring will occur at the last evaluation of progression provided by the CIBMTR.

The treatment arms will be compared with a two-sided log-rank test stratified on risk status. Tests will be performed pair-wise at the 0.05/3 level to maintain type I error at 0.05 for this endpoint in this analysis. A Kaplan-Meier plot of PFS and 5-year estimates of PFS will be provided by treatment group.

A secondary analysis of PFS will be conducted using Cox regression, with treatment arm and risk strata as covariates, and adjusting for demographic and baseline characteristics which are statistically different between treatment arms (p<0.1) for covariates specified in section 3.1. Start time will be randomization on BMT CTN 0702.

In another secondary analysis of PFS, discontinuation of lenalidomide maintenance will be considered as a time-varying covariate in a separate Cox regression model for those who initiated lenalidomide; in this model, the outcome will be the time to progression or death from initiation of lenalidomide. Initiation of maintenance lenalidomide on BMT CTN 0702 will be the start time for this analysis. CIBMTR data will be used to determine whether participants who discontinued study lenalidomide also discontinued commercial lenalidomide. The limited interpretation will be noted for this analysis, since it will include non-randomized comparisons and there may be bias in who enrolled in BMT CTN 07LT.

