Exhibit 07LT-4B: Multivariate Cox Regression Analysis of Progression-free Survival from Initiation of Lenalidomide (Secondary Analysis of PFS)

Maximum Likelihood Estimates and Hazard Ratios

		0		
Covariate	Point Estimate	Lower Confidence Limit	Upper Confidence Limit	Model Parameter Estimate p-value
Auto/Auto treatment arm vs Auto/Maintenance arm¹				
Auto/Auto treatment arm vs Auto/RVD arm ¹				
Auto/RVD treatment arm vs Auto/Maintenance arm ¹				
Risk strata—High risk vs Risk strata—Standard risk				
Permanent discontinuation of lenalidomide (time-dependent)				
(other adjustment factor as needed)				
(other adjustment factor as needed)				
(other adjustment factor as needed)				

¹ P-values are compared to the 0.05/3 significance level.

Figure: A forest plot for the hazard ratios and confidence intervals may also be provided.

Notes for this secondary analysis:

Model covariates:

[figure not shown]
- Treatment group
- Randomized risk strata
- Any of the factors in column 2 of the table in Section 3.1 that have a test for treatment group differences that is significant at the 0.1 level. ERC-adjudicated baseline disease response will be tested using 2 categorizations (CR or better, VGPR or better). If both are significant at the 0.1 level, the one that is more significant will be used in the model.
- No interactions
- Permanent discontinuation of lenalidomide as a time varying covariate.

- Analysis population is 0702 participants who initiated lenalidomide
- Time to PFS is calculated from start time of lenalidomide
- Proc phreg in SAS, no model selection procedure

Exhibit 07LT-5: Overall Survival

Figure template for illustration only

Overall Survival by Treatment Arm

Kaplan Meier Estimates and 98.3% Confidence Intervals

	Auto/Auto	Auto/RVD	Auto/Maint		
5-year Estimates:	XX.X (XX.X, XX.X)	XX.X (XX.X, XX.X)	XX.X (XX.X, XX.X)		

Stratified Log-Rank Test for Treatment Group Differences

[figure not shown]
Treatment Group Comparison	p-value ¹
Auto/Auto vs Auto/RVD	0.XX
Auto/Auto vs Auto/Maint	0.XX
Auto/RVD vs Auto/Maint	0.XX

¹Significance level is 0.05/3 for each pairwise comparison.

Exhibit 07LT-6: Event-Free Survival

Figure template for illustration only

Event-Free Survival by Treatment Arm

Kaplan Meier Estimates and 98.3% Confidence Intervals

	Auto/Auto	Auto/RVD	Auto/Maint		
5-year Estimates:	XX.X (XX.X, XX.X)	XX.X (XX.X, XX.X)	XX.X (XX.X, XX.X)		

Stratified Log-Rank Test for Treatment Group Differences

[figure not shown]

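### Coding stopping as permanent discontinuation, with no rule for the gap between 0702 and 07LT drug, can let later events set the covariate and push the hazard ratio for stopping upward

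*SAP*

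**What the plan says.** SAP 4.1 plans a secondary PFS model in which "discontinuation of lenalidomide maintenance will be considered as a time-varying covariate in a separate Cox regression model for those who initiated lenalidomide". The clock is fixed: "Initiation of maintenance lenalidomide on BMT CTN 0702 will be the start time for this analysis". Section 4.3 uses the same unqualified word for the supplemental EFS model. The model notes under Exhibits 07LT-4B and 5B narrow it to "Permanent discontinuation of lenalidomide as a time varying covariate", and the 6C table has a row for permanent discontinuation. The term is not defined for any of these models.

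SAP 1.2.2 shows that treatment could be interrupted between the two studies: "The protocol was approved after some participants had already finished 3 years of maintenance on BMT CTN 0702", and "The protocol was activated in March 2015". In between, "there may have been a period when the participant was on commercially-available lenalidomide or other treatment".

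Restarting on 07LT is conditional. Protocol 2.3.2 requires "Completion of 3 years of maintenance therapy on BMT CTN 0702", and Protocol 2.3.3 excludes "Patients who have evidence of disease progression prior to enrollment". Anyone who starts 07LT lenalidomide after a gap must therefore have come through it alive and progression-free.

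SAP 4.1 also plans to use CIBMTR data to see whether those who stopped study drug stopped commercial lenalidomide as well. It promises a caveat about non-randomized comparison and about who enrolled on 07LT.

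**The concern.** A time-varying covariate in a Cox model may use only what is known at each time. Whether a stop is permanent is not known when it happens; it depends on whether the participant later restarts. Here restart is open only to participants who have not progressed. Under that coding, progressions and deaths in the off-drug gap are charged to the discontinued state, while the event-free gap time of those who restart is credited to lenalidomide. This is guarantee-time (immortal-time) bias, and it makes stopping look harmful even if it is not.

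At stake is the hazard ratio for stopping in Exhibit 4B, a planned secondary analysis, and in the related models in 5B and 6C. The planned caveat concerns confounding and selection into 07LT. It does not cover this problem which, unlike confounding, can be removed by definition and programming.

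**Working it through.** **1. The plan's own figures.** No value is stated for the discontinuation effect. The figures that can be checked are the projected 07LT size and the pairwise alpha:
- 758 × 0.55 = 416.9 (stated 417) and 758 × 0.75 = 568.5 (stated 569). Both reproduce.
- 0.05/3 = 0.01667, as stated. In the exhibits it is footnoted to the treatment-arm rows, not to the discontinuation row.

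**2. Two participants, same stop.** Both finish 0702 drug at month 36 of maintenance and take no lenalidomide afterwards. At month 38 neither has had an event.
- A progresses at month 40. Exclusion 1 bars 07LT drug, so the stop was permanent and A is *discontinued* from month 36, with the event in that state.
- B is still progression-free at month 42 and starts 07LT drug. The stop was not permanent, so months 36–42 count as *on*.

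At month 38 their histories are identical but their covariate values differ, solely because of what happens later.

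**3. Size under no true effect.** From the documents: 3-year PFS of 55–75% and 36 months of 0702 maintenance. Assumed, because the documents do not say: 640 of the 758 start lenalidomide; 15–50% stop before 3 years; 0–100% of completers have a gap, uniform from 0 to a maximum of 6–24 months; 80–95% would restart; follow-up is 48–72 months from the start of lenalidomide. The monthly event rate is −ln(PFS at 3 years)/36, for example −ln(0.65)/36 = 0.0120. The early-stopping rate is −ln(1 − share stopping early)/36. Event times do not depend on treatment, so the true hazard ratio is 1. Each setting was run 400 times, with the term tested at two-sided 0.05; Monte Carlo error on each hazard ratio is about 0.01.

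*Look-ahead* keeps restarters *on* through the gap. *Current status* is off from the stop and on again at restart. Unless noted, 3-year PFS is 65%, 35% stop early, 80% would restart, and no gap patient takes commercial drug.

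| Share with gap, maximum length | HR look-ahead | HR current status | Rejection, look-ahead | Rejection, current status |
|---|---|---|---|---|
| None | 0.99 | 0.99 | 4% | 4% |
| 25%, 6 months | 1.04 | 1.00 | 6% | 6% |
| 25%, 12 months | 1.06 | 1.00 | 9% | 5% |
| 50%, 6 months | 1.06 | 0.99 | 8% | 6% |
| 50%, 12 months | 1.12 | 0.99 | 17% | 6% |
| 50%, 24 months | 1.20 | 1.00 | 31% | 6% |
| 100%, 12 months | 1.28 | 1.01 | 51% | 4% |
| 50%, 12 months; 15% stop early | 1.27 | 1.00 | 36% | 6% |
| 50%, 12 months; 15% stop early, 95% restart | 1.35 | 0.98 | 45% | 5% |
| 50%, 12 months; half of gap patients on commercial drug | 1.08 | 1.01 | 10% | 7% |
| 50%, 12 months; 80% on commercial drug | 1.02 | 0.99 | 7% | 6% |
| 50%, 12 months; all on commercial drug | 0.99 | 0.99 | 5% | 5% |

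In the 50%, 12-month case, changing 3-year PFS to 55% or 75% gives look-ahead hazard ratios of 1.13 and 1.14; 50% stopping early gives 1.09.

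A separate simulation (events 1.3% and early stopping 0.8% per month, 60–80% of completers wishing to continue) gave 1.01–1.08 with 15% having a gap, about 1.06–1.14 with 30% and 1.11–1.24 with 50%, against 0.96–1.02 for actual on/off status.

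**The case against.** The strongest reply is that no passage states the look-ahead rule. The body of the SAP and Protocol 5.3 say only discontinuation; the word permanent is attached to this covariate only in the appendix, whose templates SAP section 5 calls illustrative. Protocol 4.3.1 treats permanent discontinuation as a working status that settles reporting duties. If status were fixed on the day of the stop, A and B would be coded alike and the bias would vanish.

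This stands in part: a reader might infer that the SAP commits to the faulty coding, and it does not. But the notes under Exhibit 4B list the model's covariates, which is more than layout. Supplemental Exhibit 07LT-3 points to the look-ahead reading: it tabulates permanent discontinuation for those who started drug on 07LT, and moves to the commercial stop where commercial use continued. It is a table of reasons, not a coding rule, but it does not treat a 0702 stop followed by restart as the permanent one. Fixing status at the stop is also wrong, since restarters would be coded as off while taking 07LT drug.

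Second, gap time may have been spent on commercial lenalidomide. That time is rightly *on*, and the planned CIBMTR check addresses it. This stands and limits the size, but it does nothing for gap time truly off drug.

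Third, these are non-randomized secondary or supplemental models with a promised caveat, and SAP 4.3 also compares outcomes by lenalidomide status at four years among those still at risk. That landmark design does not have this fault. Both are true; neither repairs Exhibits 4B, 5B and 6C.

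**Conclusion.** The point holds as an undefined covariate whose ordinary reading uses future information and biases the hazard ratio for stopping upward. The direction follows from the restart rule. The size cannot be taken from the documents: it is about 1.0 if gaps are few or mostly covered by known commercial lenalidomide, and about 1.1–1.35 if off-drug gaps are many or long, with no true effect.

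Three stronger readings are not supported. First, a large bias cannot be asserted, because the number of gap patients, the gap lengths and the off-drug share are all unstated. Second, the trial's main conclusion is not touched: the primary log-rank test compares randomized arms and does not use this covariate. Third, the simulated figures do not carry over to overall survival in Exhibit 5B. There progression stops the drug (Protocol 2.4.1) while follow-up for death continues, so deaths after progression would fall in off time under either coding.

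**What to change.** Use one definition in SAP 4.1, 4.3 and Exhibits 07LT-4B, 5B and 6C: current lenalidomide status by date. Status is off from the last dose of 0702 or commercial drug and on again from the first 07LT or commercial dose. Every gap between 0702 and 07LT drug is coded by actual use.

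For holds within a treatment period, state a fixed grace period in advance and switch status to off only once it has elapsed. Simply ignoring short holds would bring look-ahead back, since a hold is known to be short only after it ends. The scheduled end of 0702 drug is known when it occurs and needs no grace period.

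For Exhibit 5B, add a note that recoding removes this bias but not the link between progression and stopping. Report how many participants had a gap, how long it lasted and how many took commercial lenalidomide, so that readers can judge how much the rule matters.

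The cost is SAP wording and programming. The downside is data quality: SAP 4.1 promises CIBMTR information on whether commercial lenalidomide was stopped, and some start or stop dates may be missing or imprecise.

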#### 5.2. Accrual, Registration and Follow-up

It is anticipated that approximately 450 patients will be enrolled on this protocol based on assumed estimates of PFS estimates from the BMT CTN 0702 study. The total sample size may as low as 417 if the observed 3-year PFS on the BMT CTN 0702 is 55% but may be as high as 569 if the 3-year PFS is 75%. Follow-up on this protocol will continue through December 31, 2018.

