##### **Unexpected Grades 3-5 Adverse Events**

Unexpected grades 3-5 adverse events will be tabulated and compared across treatment arms. AEs will be described using the Medical Dictionary for Regulatory Activities (MedDRA) and classified according to the system organ class and preferred term. Summaries by type and severity by treatment arm will be provided.

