2.7.2 Safety Analysis and Analysis Population

The 07LT-enrolled population is comprised of two groups of participants – those who are taking long-term lenalidomide maintenance therapy, and those who have never started maintenance therapy. Safety data is collected differently for participants taking lenalidomide and or patients who never stated lenalidomide on 07LT or discontinued it.

For participants enrolled on BMT CTN 07LT who are taking long-term lenalidomide maintenance therapy, unexpected, grades 3-5 adverse events will be reported through the expedited AE reporting system in AdvantageEDC using NCI's Common Terminology Criteria for Adverse Events (CTCAE) Version 4.0. Unexpected, grade 4-5 AEs must be reported within 24 hours of knowledge of the event. Unexpected, grade 3 AEs must be reported within three business days of knowledge of the event. Selected expected serious AEs (protocol Appendix F - Table F-1) require expedited reporting. Additionally, selected AEs of interest (protocol Appendix F - Table F-2) will require expedited reporting, if they fulfill serious criteria according to the Code of Federal Regulations Title 21 (21 CFR 312.32) and occur after the administration of lenalidomide and up to 30 days after the permanent discontinuation of lenalidomide. See protocol Appendix F for additional details on expedited reporting.

For participants enrolled on BMT CTN 07LT follow-up only, or for BMT CTN 07LT participants who have permanently discontinued lenalidomide maintenance for more than 28-30 days, or for participants who have met the protocol defined definition of progression, reporting of

unexpected grades 3-5 adverse events, selected serious AEs, or selected AEs of interest will not require reporting with the exception of second primary malignancies.

Deaths are required to be reported for all patients enrolled on 07LT within 24 hours of the site's knowledge of the patient's death.

Unexpected grades 3-5 adverse events will be tabulated and compared across treatment arms for the BMT CTN 07LT population. Summaries by type and severity of adverse events will be provided. Safety data will be summarized using Medical Dictionary for Regulatory Activities (MedDRA) Coding Version 20.0 or above.

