The event is the development of the first SPM post randomization on BMT CTN 0702, excluding non-melanoma skin cancers. Death without SPMs will be considered a competing risk for this event. The analysis population is the 0702-enrolled population, and CIBMTR data will be used to supplement BMT CTN 0702/07LT data. Start time is randomization on BMT CTN 0702. Cumulative incidence function will be used to calculate this endpoint and time of randomization on the BMT CTN 0702 protocol will be the starting point for the analysis. Estimates at 5 years will be described along with 98.3% confidence intervals. The cumulative incidence of SPMs will be compared between treatment arms using stratified two-sided Gray's test in pairwise comparisons of treatment groups. SPMs will also be described by histologic type. It will be

noted that reporting of SPM is not required after progression, and the CIBMTR data will be used to supplement 07LT data.

Unexpected Grades 3-5 Adverse Events

Unexpected grades 3-5 adverse events occurring post enrollment on BMT CTN 07LT will be tabulated and compared across treatment arms and lenalidomide status for participants enrolled in BMT CTN 07LT. CIMBTR data will not be used. AEs will be described using the Medical Dictionary for Regulatory Activities (MedDRA) and classified according to the system organ class and preferred term. Summaries by type and severity by treatment arm will be provided, and tabulations will be separated into tables for those who initiated maintenance on BMT CTN 07LT and those who did not.

Health Quality of Life

Health quality of life (HQL) will be compared between all treatment groups utilizing the FACT-BMT self-report, transplant-specific questionnaire and the generic quality of life tool, the SF-36. Only English and Spanish speaking patients are eligible to participate in the HQL component of this trial. Participants were not required to complete the HQL questionnaires after progression; therefore, only HQL completed prior to progression will be summarized. The limitations in interpretation of this analysis will be noted with the presentation of the results. HQL at each time point from BMT 0702 baseline through 5 years post randomization on BMT CTN 0702 will be summarized using simple descriptive statistics (median, mean, SD or SE). No formal statistical analyses will be conducted. As 5 year data is only available for those participants on 07LT, this analysis will focus solely on 07LT participants.

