5. Template of Proposed Table/Figure/Listing (TFL) Shells

The templates for the Tables, Figures, and Listings are provided in the Appendix of this SAP. These templates are for illustration purposes only, and may not be the final layout or wording chosen for publications or presentations. Actual format of the tables and figures may differ and will be subject to change in the final analysis report and/or publication. Editorial changes in presentation or content will not necessarily be described in the changes to planned analyses section of the report or SAP updates.

6. References

Cox D. Regression models and lifetables (with discussion). Journal of the Royal Statistical Society 1972; Series B:187-220.

Gray RJ. A class of K-sample tests for comparing the cumulative incidence of a competing risk. Annals of Statistics 1988, 16: 1141-1154.

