			F	First Event ³			
Comparison	N	Total Number with an Event	PRG or NPT	SPM	ртн	p-value ¹	
Auto/Auto to	247	XXX	XXX	XXX	XXX	0.XX	
Auto/RVD	254	XXX	XXX	XXX	XXX		
Auto/Auto to	247	XXX	XXX	XXX	XXX	0.XX	
Auto/Maintenance	257	XXX	XXX	XXX	XXX		
Auto/RVD to	254	XXX	XXX	XXX	XXX	0.XX	
Auto/Maintenance	257	XXX	XXX	XXX	XXX		

¹Significance level is 0.05/3 for each pairwise comparison.

Exhibit 07LT-7: Cumulative Incidence of First SPM

Figure template for illustration only

Cumulative Incidence of First SPM by Treatment Arm

Cumulative Incidence Estimates and 98.3% Confidence Intervals

	Auto/Auto	Auto/RVD	Auto/Maint		
5-year Estimates:	XX.X (XX.X, XX.X)	XX.X (XX.X, XX.X)	XX.X (XX.X, XX.X)		

Stratified Gray's Test for Treatment Group Differences

Treatment Group Comparison	p-value ¹
Auto/Auto vs Auto/RVD	0.XX
Auto/Auto vs Auto/Maint	0.XX
Auto/RVD vs Auto/Maint	0.XX

¹Significance level is 0.05/3 for each pairwise comparison.

Exhibit 07LT-8: SPM Histologic Type

	Au	Auto/Auto		Auto/RVD		Auto/Maint		Total
	N	%	N	%	N	%	N	%
All ¹	XXX	100.0	XXX	100.0	XXX	100.0	XXX	100.0
Hematologic SPM	XXX	XX.X	XXX	XX.X	XXX	XX.X	XXX	XX.X
High-Level Group Term 1	XXX		XXX		XXX		XXX	
High-Level Group Term 2	XXX		XXX		XXX		XXX	
(etc.)	XXX		XXX		XXX		XXX	
Solid Tumor SPM	XXX	XX.X	XXX	XX.X	XXX	XX.X	XXX	XX.X
High-Level Group Term 1	XXX		XXX		XXX		XXX	
High-Level Group Term 2	XXX		XXX		XXX		XXX	
(etc.)	XXX		XXX		XXX		XXX	

¹More than one SPM may be reported per participant. SPM reporting on BMT CTN 0702 and 07LT is not required after progression. Supplemental data is provided by the CIBMTR.

Exhibit 07LT-9A: Unexpected Grades 3-5 Adverse Events in Participants Initiating Lenalidomide on BMT CTN 07LT¹

		Auto/Auto	Auto/RVD	Auto/Maint	
		N %	N %	N %	Total
All Unexpected Grades 3-5 Adverse Events		XX 100.0	XX 100.0	XX 100.0	XX 100.0
System Organ Class	Preferred				
(SOC)	Term				
SOC1	ALL	XX XX.X	XX XX.X	XX XX.X	XX XX.X
	PT1	(just N)	(just N)	(just N)	(just N)
	PT2	(just N)	(just N)	(just N)	(just N)
SOC2	ALL	XX XX.X	XX XX.X	XX XX.X	XX XX.X
	PT1	(just N)	(just N)	(just N)	(just N)
	PT2	(just N)	(just N)	(just N)	(just N)
(etc.)	(etc.)				
Severity					
Grade 3		XX XX.X	XX XX.X	XX XX.X	XX XX.X
Grade 4		XX XX.X	XX XX.X	XX XX.X	XX XX.X
Grade 5		XX XX.X	XX XX.X	XX XX.X	XX XX.X

¹ The reporting requirements differ for participants taking lenalidomide.

Exhibit 07LT-9B: Unexpected Grades 3-5 Adverse Events in Participants Enrolled on BMT CTN 07LT Who Did Not Initiate Lenalidomide

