(6 Items)	R1Y												
	R2Y												
	R3Y												
	R4Y												
	R5Y												
Functional Well-Being	Baseline												
(7 Items)	R1Y												
	R2Y												
	R3Y												
	R4Y												
	R5Y												

Figures may also be provided.

Supplemental Exhibit 07LT-1: Enrollment

A table will be provided showing actual yearly accrual for each 07LT participating center from 07LT study initiation to accrual closure.

A table will be provided showing time to last contact summarized separately for participants enrolled on BMT CTN 07LT, and for participants not enrolled on BMT CTN 07LT.

Supplemental Exhibit 07LT-2: Significant Protocol Deviations

A table listing significant protocol deviations/violations will be provided separately for those who continued lenalidomide maintenance therapy on 07LT and those who did not, by treatment group for participants enrolled on 07LT.

Supplemental Exhibit 07LT-3: Permanent Discontinuation of Lenalidomide

A table will be provided to describe the reasons for permanent discontinuation of lenalidomide maintenance therapy for BMT CTN 0702-enrolled participants who initiated therapy on BMT CTN 07LT. For participants who have confirmed they continued on commercial lenalidomide, discontinuation data will be based on discontinuation of commercial lenalidomide.

Supplemental Exhibit 07LT-4: Primary Cause of Death

A table summarizing the primary cause of death by treatment group will be provided; the table will be separated into adjudicated deaths and unadjudicated deaths. Primary cause of death is adjudicated by the BMT CTN 0702 Endpoint Review Committee (ERC) for most participants who died within 38 months of enrollment on 0702. For deaths where cause is not adjudicated by the ERC, if the participant progressed prior to death without a secondary malignancy, cause of death will be reported as progression; if the person progressed prior to death and also reported an SPM, cause of death will be reported as progression/SPM; if the person did not progress prior to death but reported an SPM, cause of death will be reported as SPM; if the person did not progress prior to death and did not report an SPM, site-reported cause of death will be reported.

	Treatment Arm					Total		
	Auto/A	uto	Auto/RVD		Auto/Maint			
	N	%	N	%	N	%	N	%
Enrolled	247	100.0	254	100.0	257	100.0	758	100.0
Total deaths								
Deaths adjudicated by BMT CTN 0702 ERC								
Deaths not adjudicated by BMT CTN 0702 ERC								

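### The percentages in AE Exhibits 07LT-9A and 9B are shares of the reported AE total, not risks, and cannot support the promised comparison across arms

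*SAP*

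**What the plan says.** Three places in the documents promise a comparison of these events:

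- Protocol 5.4: "Unexpected grades 3-5 adverse events will be tabulated and compared across treatment arms".
- SAP 2.7.2: "Unexpected grades 3-5 adverse events will be tabulated and compared across treatment arms for the BMT CTN 07LT population".
- SAP 4.2 adds a second axis, so that events are "tabulated and compared across treatment arms and lenalidomide status for participants enrolled in BMT CTN 07LT". It splits the tables by whether lenalidomide was started on 07LT.

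No text names an AE rate, a denominator, an exposure adjustment or a test. The only detail is in the SAP Appendix. Exhibit 07LT-9A is titled "Unexpected Grades 3-5 Adverse Events in Participants Initiating Lenalidomide on BMT CTN 07LT", and 9B covers 07LT participants who did not start it. In both shells the first row, "All Unexpected Grades 3-5 Adverse Events", is preset to 100.0 in each arm and in the total column. Organ-class and grade rows have a count and a percentage; preferred terms have a count only. Neither header has a participant N.

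Supplemental Exhibit 07LT-4 is built differently. It is introduced with "A table summarizing the primary cause of death by treatment group will be provided", and its 100.0 row is enrolled participants (247, 254 and 257).

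**The concern.** A percentage in a by-arm AE table is normally read as the proportion of participants affected. Here it is the make-up of the arm's own AE total. Two arms with quite different AE burdens can show the same column of percentages. A class that affects equal proportions of participants can look very different between arms, and the direction of a difference can even reverse.

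Comparing raw counts by eye is not a safe substitute. The 9A population is selected after randomization: alive, progression-free, consenting, and having completed 3 years of maintenance. Arm sizes need not be equal. AE reporting also ends around progression or a few weeks after the last lenalidomide dose, so observation time may differ between arms. What is at stake is whether the report shows a difference in unexpected grade 3-5 AEs between randomized arms if there is one.

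**Working it through.** **1. The plan's own figure.** Let k be the entry in the all-AE row for an arm. The printed 100.0 is 100 × k/k, which holds for any k. On a base of n participants at risk, the row would be 100.0 only if every participant had an event. The base is therefore the row itself. The shell does not say whether k counts events or participants with an event; in neither case is it the number at risk.

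**2. Inputs for an illustration.** The shells contain no data, so all AE counts here are assumed, with one event per participant. For n, protocol 5.2 says that "approximately 450 patients will be enrolled on this protocol"; an equal split (assumed) gives 450/3 = 150 per arm. The stated enrolment range reproduces from the 758 randomized: 758 × 0.55 = 416.9 → 417 and 758 × 0.75 = 568.5 → 569, or 139 and about 190 per arm. Exhibit 9A covers only lenalidomide initiators, whose number is not given, so its n would be no larger than total 07LT enrolment.

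**3. A twofold risk difference that the percentages hide.**

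| | Arm A | Arm B | Shell %, A / B | % of 150 at risk, A / B |
|---|---|---|---|---|
| All | 15 | 30 | 100.0 / 100.0 | 10.0 / 20.0 |
| Grade 3 | 10 | 20 | 66.7 / 66.7 | 6.7 / 13.3 |
| Grade 4 | 4 | 8 | 26.7 / 26.7 | 2.7 / 5.3 |
| Grade 5 | 1 | 2 | 6.7 / 6.7 | 0.7 / 1.3 |

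The shell percentages do not depend on n. The overall risks become 15/139 = 10.8% and 30/139 = 21.6%, or 15/190 = 7.9% and 30/190 = 15.8%, at the ends of the enrolment range.

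**4. Equal risks that look different.** One organ class affects 10 of 150 in each arm (6.7% each), with arm totals of 15 and 40. The shell shows 10/15 = 66.7% and 10/40 = 25.0%.

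**5. A reversed direction.** One organ class has 6 of 10 events in arm A and 12 of 30 in arm B. The shell shows 60.0% and 40.0%. Per participant at risk, it is 6/150 = 4.0% and 12/150 = 8.0%.

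**6. What the other exhibits supply.** Exhibit 07LT-1 shows 07LT enrolment, treatment assignment, lenalidomide initiation and length of follow-up by arm. Exhibit 07LT-2B has a per-arm N for 07LT participants. Dividing the 9A counts by these gives a crude count per participant. No exhibit is specified to give the number of participants with at least one AE. None gives AE-reporting person-time either, and length of follow-up is no substitute, because follow-up continues after AE reporting stops.

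**7. Ascertainment in 9B.** Protocol 4.3.1 and SAP 1.5 and 2.7.2 do not require participants who are not on long-term lenalidomide to report these AEs, apart from second primary malignancies (SPMs). A participant denominator in 9B would turn incomplete data into apparent rates.

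**The case against.** The strongest reply is that the shells are not binding. SAP Section 5 says: "These templates are for illustration purposes only, and may not be the final layout or wording chosen for publications or presentations". The governing text promises tabulation, comparison and summaries by type and severity, and fixes no percentage base. That is true, and it makes the change easy. It does not remove the need, because nothing else in either document sets a participant denominator.

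Four stronger readings are tempting but not supported:

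- **That the comparison is impossible from the planned output.** The shells print raw counts down to preferred term, and Exhibits 07LT-1 and 2B supply participant numbers. The percentage column fails, not the whole output.
- **That no exhibit gives numbers at risk or follow-up.** Exhibit 07LT-1 covers both. The number at risk is missing from 9A and 9B themselves.
- **That one participant with repeated events could dominate an organ class.** This needs N to count events, which 9A and 9B do not say. The footnote allowing several reports per participant belongs to Exhibit 07LT-8.
- **That Exhibit 07LT-8 has the same fault.** It also sets its total to 100.0, but it describes SPMs by histologic type. SPM risk is compared in Exhibit 07LT-7, with 5-year cumulative incidence, 98.3% confidence intervals and stratified Gray's test. A share by type is a legitimate description there.

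**Conclusion.** The point holds for the percentages in Exhibits 07LT-9A and 9B. Their base is the arm's own AE total, so they say nothing about risk and can hide, exaggerate or reverse a difference between arms. In the illustration, 10.0% against 20.0% appears as identical columns. That size rests on assumed counts, equal arms of 150 and one event per participant; the effect on the real results cannot be calculated from the documents. The structural finding needs none of these assumptions, since k/k is 100.0 whatever is observed.

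This is a reporting defect that is worth correcting before the tables are programmed. It does not touch the primary analysis or the SPM comparison.

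**What to change.** **Exhibit 07LT-9A.** Put the number of 07LT lenalidomide initiators per arm in the column headers. Report participants with at least one event as n (% of that N) overall, by organ class, by preferred term and by worst grade, counting each participant once per row. Show event counts separately, with a rate per 100 person-years of AE-reporting time, from lenalidomide start on 07LT to the end of the protocol's AE reporting window. State the end of that window explicitly: SAP 1.5 refers to progression or 28 days from the last dose, and SAP 2.7.2 to 28-30 days after discontinuation, so the passages need to be reconciled first.

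**Exhibit 07LT-9B.** Show the participant N and counts only, with a footnote that these AEs were not required to be reported. Calculate no rates and draw no contrast with 9A. The wording in SAP 4.2 on comparison by lenalidomide status should be qualified to match.

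**Exhibit 07LT-8.** Leave it as a description by histologic type.

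**SAP 4.2.** Add one sentence defining the denominator, so that it does not rest on an illustrative shell.

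The cost is two shell edits, the small text changes above and some programming to derive AE-reporting time. The fix adds no trial procedures.
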